10.5.3 Additional Safety Analyses

Local reactogenicity at SC injection administration sites ([Appendix B](#)) will be summarized by type, toxicity grading, dose group, and time point. Skin ulcers at injection sites will be additionally summarized by size measurements and resolution. If there are multiple injection sites, the maximum severity across all injection sites will be summarized by day after injection at the respective sites.

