8.1.1 Adverse Events

ICH E6 defines an AE as any untoward medical occurrence in a patient or clinical investigation subject administered a pharmaceutical product regardless of its causal relationship to the study treatment. FDA defines an AE as any untoward medical occurrence associated with the use of a drug in humans, whether or not considered drug-related.

An AE can therefore be any unfavorable and unintended sign (including an abnormal laboratory finding), symptom, or disease temporally associated with the use of medicinal (investigational) product. The occurrence of an AE may come to the attention of study personnel during study visits and interviews of a study recipient presenting for medical care, or upon review by a study monitor.

All AEs, including solicited local (injection site), starting from administration of the first dose of study drug until the final study visit will be captured on the appropriate data DCF and eCRF. Information to be collected for AEs includes event description, date of onset, assessment of

severity, relationship to study product, and alternate etiology (assessed only by those with the training and authority to make a diagnosis and listed on Form FDA 1572 as a PI), date of resolution, seriousness and outcome. AEs occurring during the trial collection and reporting period will be documented appropriately regardless of relationship. AEs will be followed through resolution or until assessed to be stable by the PI.

Any medical condition that is present at the time that the subject is screened will be considered as baseline and not reported as an AE. However, if the severity of any pre-existing medical condition increases, it should be recorded as an AE.

Adverse Events Grading

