#### 7.3.1. Solicited Reactogenicity Symptoms

For each solicited local reactogenicity symptom, the number and percentage of subjects reporting each symptom will be summarized by maximum severity for a specified time point and Dose Group.

Maximum severity for each symptom based on functional grading and measurement grading criteria as described in protocol v6.0 will be summarized separately. All pre-dose and post-dose solicited local reactogenicity will be presented in [Listing 9](#).

The following summaries for solicited local reactogenicity symptoms will be presented:

- The number and proportion of subjects with local symptoms, summarized by Dose Group and symptom. A 95% CI will be presented by Dose Group for each local symptom ([Table 9](#)).
- The number and proportion of subjects with local symptoms, summarized by Dose Group, symptom, and maximum severity. A 95% CI will be presented by Dose Group for each local symptom ([Table 10](#)).
- The number and proportion of subjects with local symptoms, summarized by Dose Group, symptom, time point, and maximum severity (including maximum severity post-baseline) ([Table 11](#)).
- By Dose Group, bar charts of proportions of subjects with local symptoms by maximum severity (each subject counted once per symptom) ([Figure 2](#)).
- By Dose Group and time point, bar charts of proportions of subjects with each local symptom by maximum severity (starting at [Figure 3](#), continuing through [Figure 16](#)).

The following solicited local reactogenicity symptoms will be presented (in order):

- Pain, tenderness, pruritus (itching), ecchymosis (bruising) (functional grade), ecchymosis (bruising) (measurement grade), induration (hardness)/ swelling (functional grade), induration (hardness)/ swelling, (measurement grade), erythema (redness) (functional grade), erythema (redness) (measurement grade), nodule (functional grade), nodule (measurement grade), ulceration (functional grade), and ulceration (measurement grade).

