**Table 10: Number and Percentage of Subjects Experiencing Solicited Reactogenicity Symptoms with 95% Confidence Intervals by Symptom, Severity, and Dose Group**

[Implementation Note: Each subject is counted once per symptom.]

Symptom	Severity	SAD Any Dose (N=X)			SAD 1 mg (N=X)			SAD 10 mg (N=X)			Placebo (N=X)		
		n	%	95% CI	n	%	95% CI	n	%	95% CI	n	%	95% CI
Any Symptom	None	x	xx	x.x, x.x	x	xx	x.x, x.x	x	xx	x.x, x.x	x	xx	x.x, x.x
	Mild												
	Moderate												
	Severe												
Pain	None												
	Mild												
	Moderate												
	Severe												
Tenderness	None												
	Mild												
	Moderate												
	Severe												
Pruritus (Itching)	None												
	Mild												
	Moderate												
	Severe												
Ecchymosis (Bruising), Functional Grade	None												
	...												
Ecchymosis (Bruising), Measurement Grade	None												
	...												
Induration (Hardness)/ Swelling, Functional Grade	...												

Symptom	Severity	SAD Any Dose (N=X)			SAD 1 mg (N=X)			SAD 10 mg (N=X)			Placebo (N=X)		
		n	%	95% CI	n	%	95% CI	n	%	95% CI	n	%	95% CI
Induration (Hardness)/ Swelling, Measurement Grade	...												
Erythema (Redness), Functional Grade	...												
Erythema (Redness), Measurement Grade	...												
Nodule, Functional Grade	...												
Nodule, Measurement Grade	...												
Ulceration, Functional Grade	...												
Ulceration, Measurement Grade	...												
Note: N = Number of subjects in Safety Population													

**Table 11: Number and Percentage of Subjects Experiencing Solicited Reactogenicity Symptoms by Symptom, Severity, Time Point, and Dose Group**

Dose Group	Time Point	N	None		Mild		Moderate		Severe	
			n	%	n	%	n	%	n	%
Any Symptoms										
SAD Any Dose	Max Severity Post Baseline									
	Day 1, 1 h Post-Dose									
	Day 1, 4 h Post-Dose									
	Day 2									
	Day 3									
	Day 4									
	Day 5									
	Day 6									
	Day 7									
	Max Severity Day 8 to Day 14									
	Max Severity Day 15 to Day 21									
	Max Severity Day 22 to Final Visit									
SAD 1 mg	Max Severity Post Baseline									
	...									
SAD 10 mg	Max Severity Post Baseline									
	...									
Placebo	Max Severity Post Baseline									
	...									
Pain										
SAD Any Dose	...									
SAD 1 mg	...									
SAD 10 mg	...									
Tenderness										
Ecchymosis (Bruising), Functional Grade										

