### 14.3.2 Listing of Deaths, Other Serious and Significant Adverse Events

**Table 14: Listing of Serious Adverse Events**

[Implementation Note: This listing is included in the table shells document, as it is included in the body of the abbreviated CSR. If the event is ongoing (no stop date), indicate “ongoing” for the “Duration”. If more than one reason is selected for the reason reported as an SAE, list all reasons in the column, separated by a comma. In the “If Not Related, Alternate Etiology” column, merge the 2 data fields for collecting alternate etiology, separate by a colon. Listing should be sorted by Dose Group, Subject ID, and AE Number.]

Adverse Event	MedDRA System Organ Class	MedDRA Preferred Term	Study Day	Duration of AE in Days	Study Day the Event Became Serious	Reason Reported as an SAE	Severity	Relationship to Study Treatment (Alternate Etiology)	Action Taken with Study Treatment	Subject Discontinued Due to AE	Outcome
Dose Group: , Subject ID: , AE Number:											
Comments:											
Dose Group: , Subject ID: , AE Number:											
Comments:											

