**Table 15: Listing of Non-Serious, Unsolicited, Moderate or Severe Adverse Events**

[Implementation Note: This listing is included in the tables document, as it is included in the body of the abbreviated CSR. If the event is ongoing (no stop date), indicate “ongoing” in the “Duration” column. In the “If Not Related, Alternate Etiology” column, merge the 2 data fields for collecting alternate etiology, separate by a colon. Listing should be sorted by Dose Group, Subject ID, and AE Number.]

Adverse Event	MedDRA System Organ Class	MedDRA Preferred Term	Study Day	Duration of AE in Days	Severity	Relationship to Study Treatment (Alternate Etiology)	Action Taken with Study Treatment	Subject Discontinued Due to AE	Outcome
Dose Group: , Subject ID: , AE Number:									
Comments:									
Dose Group: , Subject ID: , AE Number:									
Comments:									

---

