**Figure 2: Proportions of Subjects with Solicited Reactogenicity Symptoms by Dose Group and Severity**

[Implementation Note: All local reactogenicity symptoms will be listed using consistent symptom names as the solicited reactogenicity table shells, including “Any Symptoms”]

**Figure 3: Proportions of Subjects with Solicited Reactogenicity Symptoms by Dose Group, Time Point, and Severity – Any Symptoms**

[Implementation Note: Maximum severity on Day 1 will be calculated based on all time points collected on Day 1 (Day 1, 1 h Post-Dose and Day 1, 4 h Post-Dose). Maximum severity on Day 14 and Final Visit will be calculated based on records in memory aid and in clinic assessments. ]

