**Listing 10: 16.2.7.3: Unsolicited Adverse Events**

[Implementation Note: If the event is ongoing (no stop date), indicate “ongoing” in the “Duration” column. In the “If Not Related, Alternate Etiology” column, merge the 2 data fields for collecting alternate etiology, separate by a colon. This listing includes all unsolicited adverse events. Sort order: Dose Group, Subject ID, AE Number.]

Adverse Event	MedDRA System Organ Class	MedDRA Preferred Term	Study Day	Duration of AE in Days	Severity	SAE?	Relationship to Study Treatment (Alternate Etiology)	Action Taken with Study Treatment	Subject Discontinued Due to AE	Outcome
Dose Group: , Subject ID: , AE Number:										
Comments:										
Dose Group: , Subject ID: , AE Number:										
Comments:										

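### The SAP does not carry over the protocol's planned summary of injection-site ulcers by measured size and resolution, and does not record the omission

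*Protocol*

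**What the plan says.** Protocol 10.5.3 first plans summaries of local reactogenicity by type, grade, dose group and time point. It then adds for ulcers alone: "Skin ulcers at injection sites will be additionally summarized by size measurements and resolution".

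The protocol also plans to collect what this needs. Section 7.1.4 has ulcers measured and photographed, and has healing recorded as an ungraded lesion state. Section 8.1.1 lists, among the items recorded for adverse events including solicited local ones, "date of resolution, seriousness and outcome". Section 8.1.3 has ulcers followed until they resolve.

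SAP 7.3.1 treats ulceration as one of the solicited symptoms. Its list ends "nodule (functional grade), nodule (measurement grade), ulceration (functional grade), and ulceration (measurement grade". Table 8 counts subjects with any ulceration. Tables 9 to 11 and Figures 2, 15 and 16 show ulceration by occurrence or maximum grade. Listing 9 prints each measurement beside its grade and has no outcome column.

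Protocol section 10 says that departures from the protocol's analysis will be set out in the SAP. SAP section 11 records only the early termination and the restriction to the 1 mg and 10 mg dose groups.

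**The concern.** Injection-site ulceration is the local reaction that the protocol watches most closely. It is an adverse event of special interest (8.1.3) and a named example of an event that may be judged serious (8.1.2). At any grade it stops dosing or escalation under each of 8.7.1, 8.7.2 and 8.7.3. Reversal was also a question in the repeat-dose monkey study described in protocol 3.1.2, where lesions had reversed after four weeks in all but one high-dose animal.

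For such a reaction, how large it became and whether and when it healed say more than its maximum grade. If the SAP is programmed exactly as written, the report's summaries cannot state how many ulcers healed, or on what day. Nothing in the SAP would alert the report's author that the protocol had asked for this.

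**Working it through.** No computed figure in the plan bears on this point, so the check sets the protocol's commitment against the SAP's outputs.

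**Size.** Appendix B grades an ulcer's measurement as Grade 1 at 1–50 mm, Grade 2 at 51–100 mm and Grade 3 above 100 mm. An ulcer that shrinks from 50 mm to 1 mm stays in Grade 1, so no measurement-grade entry in Tables 9 to 11 or Figure 16 changes. Values in mm appear only in Listing 9.

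**Resolution.** Three SAP outputs have both a Duration and an Outcome column:

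- Table 14, "Listing of Serious Adverse Events": a non-serious ulcer is outside it.
- Table 15, "Listing of Non-Serious, Unsolicited, Moderate or Severe Adverse Events": a solicited ulcer is outside it.
- Listing 10, whose shell says "This listing includes all unsolicited adverse events": a solicited ulcer is outside it.

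SAP 7.3.2 does say that all AEs go to Listing 10. That sentence stands in the section on unsolicited events, however, and the shell's title and note both limit the listing to them. Of the 3 outputs, 0 cover a non-serious solicited ulcer.

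**Can Table 11 stand in for resolution?** It shows maximum grade by time point, with a None column. Its last row is "Max Severity Day 22 to Final Visit". That runs from Day 22 to Day 30, 30 − 22 + 1 = 9 days (8 to 10 with the ±1 day window). The Figure 3 shell, which Figures 15 and 16 repeat, says: "Maximum severity on Day 14 and Final Visit will be calculated based on records in memory aid and in clinic assessments".

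- If a Memory Aid or unscheduled record shows the ulcer open during that window, an ulcer healed before the final visit prints the same as one still open at that visit.
- If there is no such record, the row rests on the final examination and the two print differently.

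How often the Memory Aid is completed is left to the Manual of Procedures, which is not among the documents, so the first case is possible but not certain. In both cases the row ends at the final visit, although 8.1.3 follows ulcers to resolution.

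**Number affected.** By protocol Table 1, Cohort 1 has 3 active + 1 placebo = 4 subjects and Cohort 2 has 6 + 2 = 8. The total is 4 + 8 = 12 planned subjects, of whom 3 + 6 = 9 are on active drug.

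**The case against.** **The change was disclosed.** The SAP preface says that the full SAP foreseen in the protocol was not approved before study closure and that the sponsor deemed it not required. It says this document suffices for an abbreviated report. The duty in protocol section 10 arguably belonged to that full SAP. This stands in part: the general replacement is open, and a reader should not infer concealment. But this is the only analysis plan, and its section 11 is headed as the summary of changes to planned analyses and does not mention the ulcer summary. The preface asks the report to explain departures from this SAP only, so nothing prompts an explanation of an analysis lost between protocol and SAP.

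**An ulcer would be reported as serious.** One so reported reaches Table 14 with Duration and Outcome, and the placeholder for report narratives probably covers it too. This stands for such ulcers. It does not cover every ulcer: seriousness is a medical judgment under 8.1.2, 8.1.3 provides for special-interest events deemed non-serious, and 8.7.1 lists any SAE and any ulceration as separate halting triggers.

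**Size is summarized.** It is, in grade bands. But the protocol's size summary is additional to its grade summary, so the bands meet it only in part.

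**Stronger readings that the documents do not support.** A reader might infer from the Day 14 and Day 30 clinic visits that healing could not be dated. Those are routine visits. Under 8.1.3 ulcers are assessed daily in the unit and then at a frequency set by the investigator, and 6.4.9 refers reported site changes to an unscheduled visit. A reader might also treat the absence of healing and scarring from the SAP's symptom list as a defect in itself. Both states are recorded but ungraded, so they do not belong in grade tables, and 10.5.3 asks for no scar summary.

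**Conclusion.** The point holds. A protocol-planned descriptive analysis of a halting event is not delivered: resolution is absent for any ulcer not reported as an SAE, and measured size is reduced to grade bands outside Listing 9. The omission is not itemized anywhere in the SAP.

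The size of the problem is modest. The study is descriptive and terminated, with only two cohorts, and a careful reader could partly reconstruct an ulcer's course from Listing 9. The change is still worth making before programming, because it costs little and restores what the protocol promised.

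The conclusion assumes that the shells are programmed as written and that at least one ulcer could be classed as non-serious. Because the study stopped for safety concerns, a reader might infer that ulcers were the cause and that the summary was dropped for that reason. The documents do not say what the concerns were or whether any ulcer occurred, so neither inference is supported.

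**What to change.** Add one short by-subject ulcer table to the SAP, with these columns:

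- onset day;
- maximum diameter in mm;
- resolution status;
- day resolved, meaning the first day on which the lesion is recorded as Healed under protocol 7.1.4.

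Include unscheduled visits and follow-up after Day 30. Show a lesion that has stabilized without healing separately, because protocol 8.5 also counts a stable condition as resolved if it is expected to remain chronic. If no ulcer occurred, one line saying so is enough. If the sponsor chooses not to produce the summary in the abbreviated report, SAP section 11 should say so and why.

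The cost is slight extra programming for at most 12 planned subjects, from lesion states, measurements and resolution dates already planned for collection. The one real task is bringing late ulcer follow-up into the analysis dataset. No protocol amendment is needed.

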10.5.4 PK Analysis Plan

PK profiles for rezafungin in plasma samples from all subjects who received at least one dose of rezafungin will be analysed for concentration of rezafungin (except Cohort 1) by a validated LC-MS/MS method. The following PK parameters will be estimated, by noncompartmental analysis methods using version 7.0 or higher of Phoenix WinNonlin®, for rezafungin concentrations in plasma.

C_{\max} : The maximum concentration occurring at T_{\max} ,

T_{\max} : The time of maximum observed concentration sampled during a dosing interval,

AUC_{last} : The area under the curve (AUC) from the time of dosing to the last measurable concentration,

AUC extrapolated to infinity from the observed value of the last non-zero [or last quantifiable] concentration, ,

AUC_{0-168} : The AUC over the interval from time of first dose to 168 h after first dose (for Part 2 MAD only),

$t_{1/2}$: Terminal half-life,

λ_z : The first order rate constant associated with the terminal (log-linear) portion of the curve,

CL : The total body clearance for intravenous administration,

CL/F : The total body clearance for SC administration divided by the fraction of dose absorbed,

V_z : The volume of distribution associated with the terminal slope following IV administration

V_z/F : The volume of distribution associated with the terminal slope following SC administration divided by the fraction of dose absorbed,

F: The absolute BA will be calculated as the ratio of AUC_{inf} for the SC injection and the IV infusion of rezafungin administration (Part 3),

Dose proportionality for SAD and MAD in terms of C_{max} and AUC will be assessed using a power model,

AR: Drug observed accumulation ratio (Part 2)

Other PK parameters may be estimated as appropriate. Additional details for analysis of PK endpoints will be provided in the SAP.

11 SOURCE DOCUMENTS AND ACCESS TO SOURCE DATA/DOCUMENTS

The site will maintain appropriate medical and research records in compliance with ICH E6, Section 4.9 and regulatory and institutional requirements for the protection of confidentiality of subjects. The site will permit authorized representatives of the DMID, its designees, and appropriate regulatory agencies to examine (and when required by applicable law, to copy) clinical records for the purposes of QA reviews, audits, and evaluation of the trial safety and progress. These representatives will be permitted access to all source data and source documents, which include, but are not limited to, hospital records, clinical and office charts, laboratory notes, memoranda, subjects' memory aid or evaluation checklists, pharmacy dispensing records, recorded data from automated instruments, copies or transcriptions certified after verification as being accurate and complete, microfiches, photographic negatives, microfilm or magnetic media, x-rays, and subject files and records kept at the pharmacies, laboratories, and medico-technical departments involved in the clinical trial.

11.1 Compliance with Standards of Medical Research/Deviations

This protocol will be conducted in accordance with applicable ICH guidelines and GCP. Any instance of noncompliance with the protocol will result in a documented deviation. If a change is deemed necessary to protect the safety, rights or welfare of a subject, the Sponsor and IRB/IEC will be notified as soon as possible and preferably before introducing the deviation.

12 **QUALITY CONTROL AND QUALITY ASSURANCE**

Following a written DMID-accepted Program Quality Management Plan (cQMP), the participating site and its subcontractors are responsible for conducting routine quality assurance (QA) and quality control (QC) activities to internally monitor study progress and protocol compliance. The site principal investigator will provide direct access to all study-related sites, source data/data collection forms, and reports for the purpose of monitoring and auditing by the sponsor, and inspection by local and regulatory authorities. The site principal investigator will ensure all study personnel are appropriately trained and applicable documentations are maintained on site.

The SDCC will implement quality control procedures beginning with the data entry system and generate data quality control checks that will be run on the database. Any missing data or data anomalies will be communicated to the participating site(s) for clarification and resolution.

DMID-designated clinical monitors will verify that the clinical trial is conducted, and data are generated, documented (recorded), and reported in compliance with the protocol, ICH/GCP guidelines, and the applicable regulatory requirements. Clinical monitoring reports will be submitted to DMID.

To ensure compliance with GCP and all applicable regulatory requirements, the Sponsor may conduct a quality assurance assessment and/or audit of the site records, and the regulatory agencies may conduct a regulatory inspection at any time during or after the completion of the study. In the event of an assessment, audit or inspection, the Investigator (and institution) must agree to grant the advisor(s), auditor(s), and inspector(s) direct access to all relevant documents and to allocate their time and the time of their staff to discuss the conduct of the study, any findings/relevant issues, and to implement any corrective and/or preventative actions to address any findings/issues identified.

13 DATA HANDLING AND RECORD KEEPING

13.1 Data Management Responsibilities

The investigator is responsible to ensure the accuracy, completeness, legibility, and timeliness of the data reported. All source documents should be completed in a neat, legible manner to ensure accurate interpretation of data. Black or blue permanent ink is required to ensure clarity of reproduced copies. When making changes or corrections, cross out the original entry with a single line, and initial and date the change. DO NOT ERASE, OVERWRITE, OR USE CORRECTION FLUID OR TAPE ON THE ORIGINAL.

Copies of the eCRF will be provided for use as source data collection forms and maintained for recording data for each subject enrolled in the study. Data reported in the eCRF derived from source data collection forms should be consistent or the discrepancies should be explained.

The sponsor and/or its designee will provide guidance to the site principal investigators and other study personnel on making corrections to the data collection forms and eCRF.

Training will be provided for the Electronic Data Capture (EDC) system. All personnel using the EDC system must have the appropriate education, training, and experience, or any combination thereof. The Investigator will be provided with standard operating procedures (SOPs) (contained in the SPM or a vendor-specific SOP) on the use of the EDC system. Documentation for employee education, training, and previous experience that pertains to the EDC system must be present in the Investigator files.

If electronic data systems other than those provided and maintained by the Sponsor are used for documentation and data capture, the Investigator must ensure that the systems are validated and ensure regular data back-up.

The eCRF will be signed by the Investigator or a Sub-Investigator listed on the FDA 1572 form. It is the responsibility of the Investigator to ensure the eCRFs are completed and submitted to the Sponsor (or designee) in an accurate and timely manner. The processing of eCRFs will include an audit trail (to include changes made, reason for change, date of change, and person making change). At the completion of the study, the Sponsor will be provided with a final copy of each eCRF.

Management of clinical data will be performed in accordance with applicable Sponsor standards and data cleaning procedures to ensure the integrity of the data (e.g., removing errors and inconsistencies in the data). Adverse events and concomitant medications will be coded using the MedDRA® and World Health Organization Drug (WHO DD) dictionaries respectively. Medical Electronic CRFs will be retained by the Sponsor and copies will be sent to the Investigator to maintain as the Investigator copy.

